9.2.6. Genotype Analysis

Data on the mutation type for each subject will be listed only.

Sponsor: BPL

Protocol: 8VWF07

Version: 1.0

Statistical Analysis Plan

10. SAFETY

Safety data will be summarised using the Safety Population. No formal hypothesis testing will be carried out.

The following will be used to assess the safety of Optivate®:

- Adverse events
- Viral serology
- Physical/medical examination
- Inhibitor development (although this is a safety measurement and will be assessed as the primary efficacy endpoint)

10.1. TREATMENT COMPLIANCE

Treatment compliance will not be assessed.

10.2. ADVERSE EVENTS

Adverse events will be coded to system organ classes and preferred terms using MedDRA version 16.1.

Treatment emergent AEs are defined as events that have onset following the first infusions of Optivate®, or events present before the first infusion of Optivate®, but which worsen in severity following the first infusion of Optivate®. Should the time of onset be missing, but the date of onset be equal to the date of first dosing with Optivate®, then it will be assumed such events are treatment emergent.

Should the day of onset be missing, for the purposes of assigning treatment emergence, the day will be taken to be 01, unless the month and year are the same as the month and year of first infusion of Optivate[®], in which case the date of first infusion of Optivate[®] will be taken.

Should the day and month be missing, for the purposes of assigning treatment emergence, the day and month will be taken to be 01 January, unless the year is the same as the year of first infusion of Optivate®, in which case the date of first infusion of Optivate® will be taken.

All adverse events will be listed, however only treatment emergent adverse events will be included in the summary tables.

Sponsor: BPL

Protocol: 8VWF07

Version: 1.0

Statistical Analysis Plan

Where severity or causality is missing for an event, for the purposes of the tables, these will be assumed to be severe and very likely/certain respectively. Similarly, where severity or causality changes during the course of the event, the worst case will be taken for the analysis.

Summary tables presenting frequency of AEs by SOC and PT will be ordered by overall descending frequency of SOC and then, within a SOC, by overall descending frequency of PT.

The following tables of adverse events will be produced:

- An overall summary of the number and percentage of subjects reporting TEAEs, serious TEAEs, treatment related TEAEs, TEAEs leading to withdrawal and TEAEs leading to death
- TEAEs overall and by system organ class and preferred term
- Study treatment related TEAEs overall and by system organ class and preferred term. Study-treatment related events are those recorded as having a possible, probable, or very likely/certain causality related to Optivate®.
- TEAEs by maximum severity, overall and by system organ class and preferred term
- Serious TEAEs, overall and by system organ class and preferred term
- Study treatment related serious TEAEs overall and by system organ class and preferred term. Study-treatment related events are those recorded as having a possible, probable, or very likely/certain causality related to Optivate[®].
- TEAEs by maximum relationship to study treatment, overall and by system organ class and preferred term
- TEAEs leading to drug withdrawal, overall and by system organ class and preferred term

Where a subject has multiple events within a given system organ class or preferred term, the subject will only be counted once within that system organ class or preferred term.

For summaries by severity or relationship to study treatment, where a subject has multiple events within a given system organ class or preferred term, the subject will

Sponsor: BPL

Protocol: 8VWF07

Version: 1.0

Statistical Analysis Plan

only be counted once at the maximum severity/worst case relationship at which an event occurred within that system organ class or preferred term.

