2. DETECTING ADVERSE EVENTS

Subjects will be carefully monitored for adverse events that occur after the Informed Consent Form (ICF) has been signed until the last day of the study. The Investigator or delegate will question the subjects about adverse events using a non-leading question such as "How are you feeling?" The Investigator will also record adverse events reported spontaneously by the subjects. Clinically significant changes in the findings of physical examination, and clinically significant abnormalities in the result of objective tests (e.g. laboratory variables, ECG) may also be recorded as AEs. The Investigator will use the following criteria when deciding whether to report an abnormal result as an adverse event:

- 1. The test result is associated with accompanying symptoms.
- 2. Results of additional diagnostic tests cause concern or necessitate medical intervention.
- 3. As a consequence of the test result, the dose administered to the subject is changed, the subject is withdrawn, or the subject is given concomitant treatment.
- 4. The Investigator considers the result to constitute an AE.

If any of the above criteria are met, the Investigator will report the results as an AE.

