8.4. PRIOR AND CONCOMITANT MEDICATIONS

Prior and concomitant medications will be coded to the preferred name using WHO Drug version 1 March 2013. Note, prior medications do not include FVIII containing products and/or blood products taken prior to entering the study. These are listed separately.

Prior medications are defined as those medications started prior to the date of the first infusion of Optivate[®]. Concomitant medications are those taken on or after the date of the first infusion of Optivate[®]. Note, a medication started prior to but continuing after the first infusion of Optivate[®] will be classed as both prior and concomitant.

Should the start day of the medication be missing, for the purposes of assigning prior/concomitant status, the day will be taken to be 01, unless the month and year are the same as the month and year of first infusion of Optivate®, in which case the date of first infusion of Optivate® will be taken.

Should the start day and month be missing, for the purposes of assigning prior/concomitant status, the day and month will be taken to be 01 January, unless the year is the same as the year of first infusion of Optivate[®], in which case the date of first infusion of Optivate[®] will be taken.

All medications will be listed in order of start date. The listing will identify prior medications.

Prior and concomitant medications will be summarised separately for the Safety Population. Summaries will show the number and percent of subjects taking medications coded to the given preferred term. Summary tables will be sorted alphabetically by preferred name.

Sponsor: BPL

Protocol: 8VWF07

Version: 1.0

Statistical Analysis Plan

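### SAP 10.2 dates a partial adverse event onset to the first Optivate infusion without consulting the stop date, so a run-in event known to have ended earlier can be counted as treatment-emergent (minor).

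*SAP*

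**What the plan says.** SAP 10.2 gives the basic definition: "Treatment emergent AEs are defined as events that have onset following the first infusions of" Optivate, with a second limb for events already present that worsen after that infusion. Protocol 10.7.1 likewise limits treatment-emergent events to those starting after Optivate dosing. Only treatment-emergent events enter the summary tables; all events are listed.

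SAP 10.2 then handles incomplete onset dates:

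- **Day missing.** "Should the day of onset be missing, for the purposes of assigning treatment emergence, the day will be taken to be 01, unless". An exception is made where "the month and year are the same as the month and year of first infusion of" Optivate; the first-infusion date is then used.
- **Day and month missing.** "the day and month will be taken to be 01 January, unless the year is the same as the year of first infusion of" the product. Again the first-infusion date is then used.
- **Time missing on the first day.** "Should the time of onset be missing, but the date of onset be equal to the date of first dosing with" Optivate, the event is assumed to be treatment-emergent.

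SAP 8.4 repeats the date rule for medications ("Should the start day of the medication be missing, for the purposes of assigning prior/concomitant status"). It defines prior medications by a start before the first infusion, and concomitant medications by use on or after it.

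Events are collected before Optivate is given. Protocol Appendix I, section 2, covers "adverse events that occur after the Informed Consent Form (ICF) has been signed until the last day of the study", and Protocol 7.1.3 has subjects record events in the diary while still on their current FVIII. Resolution dates are collected (Protocol Appendix I, sections 1.1 and 2.1).

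**The concern.** Assigning an event to treatment when its timing is unknown is ordinary caution. The difficulty is that the rule also applies when the timing is known. If an event stopped before the first infusion, it cannot have started after that infusion, nor worsened after it, whatever its onset day. The rule nevertheless gives it an onset date later than its stop date and places it in the treatment-emergent tables.

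Tolerability is a secondary objective (SAP 3.2). The study has one arm and about a dozen subjects, so no control column would show the same distortion and a single misplaced event is visible in a percentage. The medication rule has the same form and the same gap.

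**Working it through.** The documents give no figure on this point, so there is nothing to reproduce. The check applies the rule to test records and then measures its reach.

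**1. The rule on test records.** Take an illustrative first infusion on 20 June 2015.

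| Onset as recorded | Stop | Onset used by SAP rule | Treatment-emergent, as written | With a stop-date check |
|---|---|---|---|---|
| June 2015, day missing | 12 June | 20 June | yes | no |
| 2015, day and month missing | 12 June | 20 June | yes | no |
| June 2015, day missing | 25 June | 20 June | yes | yes |
| June 2015, day missing | missing | 20 June | yes | yes |
| May 2015, day missing | 12 June | 1 May | no | no |
| 10 June 2015 | 12 June | 10 June | no | no |

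Only the first two rows change. Fully dated events and ambiguous ones are unaffected. SAP 7.3 states that missing data are not imputed and that all available data are used; it does not add a stop-date condition to SAP 10.2.

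**2. Records moved by the rule.** Inputs: a run-in of 28 days (Protocol 7.2, Visit 1 within 4 weeks of Screening). Assumptions: Visit 1 (V1) spread evenly over a 365-day year, and onset spread evenly over the run-in. If V1 falls on day d of a month, min(d − 1, 28) run-in days lie in the same month.

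- 31-day month: 0 + 1 + … + 28 + 28 + 28 = 462
- 30-day month: 406 + 28 = 434
- February: 0 + 1 + … + 27 = 378
- Year: 7 × 462 + 4 × 434 + 378 = 5,348
- Share: 5,348 / (365 × 28) = 5,348 / 10,220 = 0.523

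So about 52% of run-in records with a missing day are moved to the first infusion. A count over a four-year calendar gives about 75% for a 14-day run-in and 26% for 56 days (Protocol 7.2 allows up to 8 weeks with repeated screening). For records with only a year, the 28-day share is 1 − 406 / 10,220 = 0.960.

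**3. Records wrongly classified.** A moved record is wrong only if the event also ended before V1. For an event whose stop is D days after onset, the count becomes max(0, min(d − 1, 28) − D). The durations are assumptions.

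- D = 3: 7 × 375 + 4 × 350 + 300 = 4,325; 4,325 / 10,220 = 42%
- D = 7: 7 × 273 + 4 × 252 + 210 = 3,129; 3,129 / 10,220 = 31%
- D = 14: 7 × 133 + 4 × 119 + 91 = 1,498; 1,498 / 10,220 = 15%

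The denominator is day-missing run-in records, not all adverse events.

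**4. Effect of one subject.** SAP 4.3 plans 12 enrolled for 10 evaluable: 100 / 12 = 8.3 and 100 / 10 = 10.0 percentage points.

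**5. Medications.** For a drug with start day missing in the V1 month and a stop before V1, the imputed start equals the first infusion. The drug is then not prior, because its start is not before the infusion. On the wording of SAP 8.4 it is not concomitant either, because it was not taken on or after that date. A program that compares only the imputed start with the infusion date would call it concomitant.

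**The case against.** The strongest reply is that the trigger is rare. It needs a run-in event with a partial onset in the V1 month or year, together with a stop date that precedes the first infusion. The documents work against that. Subjects are trained on the diary before use (Protocol 7.1.3), incomplete entries are followed up at Visit 1 (7.2.1), and missing data are queried in writing (10.2). A subject who can date the end of a recent event but not its start, even when asked, would be unusual. This stands, and it limits the weight of the point.

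Two further replies also stand. The error is conservative: it can add events to the Optivate tables but not hide any, in keeping with the worst-case handling of missing severity and causality. And it is visible: every event is listed, missing date parts print as dashes (SAP 14.2.5.3), and outputs are double-programmed and reviewed (SAP 15). None of this makes the rule right. A programmer who added the check unprompted would be departing from the SAP as written.

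A reader might infer three stronger things that the documents do not support:

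- **That about half of run-in events are misclassified.** The 52% is the share of day-missing records that the rule moves, including events still ongoing at Visit 1 that the rule may place correctly.
- **That a drug stopped before Visit 1 becomes concomitant.** SAP 8.4 defines that class by use, so the outcome is loss of prior status and an unclear class.
- **That misplaced events will also appear as treatment-related.** SAP 10.2 says "Where severity or causality is missing for an event, for the purposes of the tables, these will be assumed to be severe" and very likely or certain respectively, but this needs a second blank field that the investigator is expected to complete. Treating unassignable causality as related is also a Protocol 10.7.1 decision, separate from the date rule.

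**Conclusion.** The point holds as a minor defect. As written, SAP 10.2 classes as treatment-emergent a run-in event that has a partial onset date and a recorded stop before the first infusion, which neither the SAP's nor the protocol's definition allows. It does not affect fully dated run-in events or the primary inhibitor endpoint, and it cannot understate Optivate events.

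The number of affected records is not given and may be zero. If one subject is affected, an incidence row rises by 8.3 to 10 percentage points. The 42%, 31% and 15% rest on a 28-day run-in, evenly spread visit and onset dates, and assumed event durations of 3, 7 and 14 days. In SAP 8.4 the consequence is confined to descriptive medication tables: prior status is wrongly lost and the remaining class is ambiguous.

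**What to change.** Add to SAP 10.2: *If a complete or partial stop date shows the event ended before the first Optivate infusion, it is not treatment-emergent, whatever the imputed start date.*

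Add to SAP 8.4: *A medication whose stop date is before the first Optivate infusion is prior only, whatever the imputed start date.*

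Events with no stop date, or with a stop on or after the day of the first infusion, stay as the SAP now treats them. The cost is one sentence in each section and one condition in each derivation; the event stop dates are already collected. It should be settled before database lock, so that no record is reclassified after the data have been seen.

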10.3. VIRAL SEROLOGY

Viral serology will be assessed by the central safety laboratory. Serum samples for all viral serology testing will be collected pre-dose at the Baseline Visit (Visit 1) and at the End of Study Visit (Visit 4).

All viral serology data will be listed.

Summary tables will present the number of subjects with positive and negative serology results at each visit. A shift table will also be presented cross tabulating the results at Baseline Visit and End of Study.

10.4. PHYSICAL/MEDICAL EXAMINATION

A physical examination is performed at Screening and at Visit 4. At Screening any abnormal findings are recorded on the medical history page. At Visit 4 any abnormal findings are recorded as adverse events.

Data as to whether or not the physical examination was performed and whether there were any changes at Visit 4 from Screening will be listed only. Actual physical examination abnormalities will be summarised and listed with the medical history (Screening physical examination) and adverse event (Visit 4 physical examination) data.

Height and weight data will be listed only.

Sponsor: BPL

Protocol: 8VWF07

Version: 1.0

Statistical Analysis Plan

11. INTERIM ANALYSES

There is no planned interim analysis.

Sponsor: BPL

Protocol: 8VWF07

Version: 1.0

Statistical Analysis Plan

12. CHANGE FROM ANALYSIS PLANNED IN PROTOCOL

There are no changes to the analyses planned in the protocol.

Sponsor: BPL

Protocol: 8VWF07

Version: 1.0

Statistical Analysis Plan

14. PROGRAMMING CONSIDERATIONS

All tables, data listings, figures (TLFs), and statistical analyses will be generated using SAS® for Windows, Release 9.3 (SAS® Institute Inc., Cary, NC, USA). Computergenerated table, listing and figure output will adhere to the following specifications.

14.1. GENERAL CONSIDERATIONS

- A separate SAS® program will be created for each output.
- Each output will be stored in a separate file.
- Output files will be delivered in Word format.
- Numbering of TFLs will follow ICH E3 guidance.

14.2. TABLE, LISTING, AND FIGURE FORMAT

14.2.1. General

- All TLFs will be produced in landscape format, unless otherwise specified.
- All TLFs will be produced using the Courier New font, size 8
- The data displays for all TLFs will have a 1.5-inch binding margin on top of a landscape oriented page and a minimum 1-inch margin on the other 3 sides.
- Headers and footers for figures will be in Courier New font, size 8.
- Legends will be used for all figures with more than 1 variable, group, or item displayed.
- TLFs will be in black and white (no color), unless otherwise specified
- Specialised text styles, such as bolding, italics, borders, shading, and superscripted and subscripted text, will not be used in the TLFs, unless otherwise specified. On some occasions, superscripts 1, 2, or 3 may be used (see below).
- Only standard keyboard characters will be used in the TLFs. Special characters, such as non-printable control characters, printer-specific, or font-specific characters, will not be used. Hexadecimal-derived characters will be used, where possible, if they are appropriate to help display math symbols (e.g., μ). Certain subscripts and superscripts (e.g., cm², C_{max}) will be employed on a case-by-case basis.
- Mixed case will be used for all titles, footnotes, column headers, and programmersupplied formats, as appropriate.

Sponsor: BPL

Protocol: 8VWF07

Version: 1.0

Statistical Analysis Plan

14.2.2. Headers

• All output should have the following header at the top left of each page:

Bio Products Laboratory Limited

Protocol 8VWF07

Study Medication: Optivate®

- All output should have Page n of N at the top or bottom right corner of each page. TLFs should be internally paginated in relation to the total length (i.e., the page number should appear sequentially as page n of N, where N is the total number of pages in the table).
- The date (date output was generated) should appear along with program name and location as the last footer on each page.

14.2.3. Display Titles

• Each TLF should be identified by the designation and a numeral. (i.e., Table 14.1.1). A decimal system (x.y and x.y.z) should be used to identify TLFs with related contents. The title is centered. The analysis population should be identified on the line immediately following the title. The title and table designation are single spaced. A solid line spanning the margins will separate the display titles from the column headers. There will be 1 blank line between the last title and the solid line.

Table x.y.z
First Line of Title
Second Line of Title if Needed
ITT Population

14.2.4. Column Headers

- Column headings should be displayed immediately below the solid line described above in initial upper-case characters.
- In the case of efficacy tables, the variable (or characteristic) column will be on the
 far left followed by the treatment group columns and total column (if applicable).
 P-values may be presented under the total column or in separate p-value column (if
 applicable). Within-treatment comparisons may have p-values presented in a row
 beneath the summary statistics for that treatment.
- For numeric variables, include "unit" in column or row heading when appropriate.
- Population sizes will be presented for each treatment group in the column heading as (N=xx) (or in the row headings if applicable). This is distinct from the 'n' used for

Sponsor: BPL
Protocol: 8VWF07

Version: 1.0

Statistical Analysis Plan

the descriptive statistics representing the number of subjects in the population with the respective data.

• The order of treatments in the tables and listings will be Placebo first in the case of placebo controlled studies and Active comparators first in the case of active comparator trials, followed by a total column (if applicable).

14.2.5. Body of the Data Display

14.2.5.1. General Conventions

Data in columns of a table or listing should be formatted as follows:

- alphanumeric values are left-justified;
- whole numbers (e.g., counts) are right-justified; and
- numbers containing fractional portions are decimal aligned.

14.2.5.2. Table Conventions

- Units will be included where available
- If the categories of a parameter are ordered, then all categories between the maximum and minimum category should be presented in the table, even if n=0 for all treatment groups in a given category that is between the minimum and maximum level for that parameter. For example, the frequency distribution for symptom severity would appear as:

Severity	N
Rating	
severe	0
moderate	8
mild	3

Where percentages are presented in these tables, zero percentages will not be presented and so any counts of 0 will be presented as 0 and not as 0 (0%).

- Unless otherwise specified in the mock table, where the categories are not ordered (e.g., Medical History, Reasons for Discontinuation from the Study, etc.), then only those categories for which there is at least 1 subject represented in 1 or more groups should be included.
- Unless otherwise specified, the estimated mean and median for a set of values should be printed out to 1 more significant digit than the original values, and standard deviations should be printed out to 2 more significant digits than the

Sponsor: BPL
Protocol: 8VWF07

Version: 1.0

Statistical Analysis Plan

original values. The minimum and maximum should report the same significant digits as the original values. For example, for systolic blood pressure:

N	XX
Mean	XXX.X
Std Dev	X.XX
Median	XXX.X
Minimum	XXX
Maximum	XXX

- P-values should be output in the format: "0.xxx", where xxx is the value rounded to 3 decimal places. Any p-value less than 0.001 will be presented as <0.001. If the p-value should be less than 0.0001 then present as <0.0001. If the p-value is returned as >0.999 then present as >0.999
- Percentage values should be printed to one decimal place, in parentheses with no spaces, one space after the count (e.g., 7 (12.8%), 13 (5.4%)). Unless otherwise noted, for all percentages, the number of subjects in the analysis population for the treatment group who have an observation will be the denominator. Percentages after zero counts should not be displayed and percentages equating to 100% should be presented as 100%, without any decimal places.
- The percentage of subjects is normally calculated as a proportion of the number of subjects assessed in the relevant treatment group (or overall) for the analysis population presented. However, careful consideration is required in many instances due to the complicated nature of selecting the denominator, usually the appropriate number of subjects exposed.
- For categorical summaries (number and percentage of subjects) where a subject can be included in more than one category, describe in a footnote or programming note if the subject should be included in the summary statistics for all relevant categories or just 1 category and the criteria for selecting the criteria.
- Where a category with a subheading (such as system organ class) has to be split over more than one page, output the subheading followed by "(cont)" at the top of each subsequent page. The overall summary statistics for the subheading should only be output on the first relevant page.

